Hota et al. evaluated 57 women undergoing urogynecologic surgeries for pelvic organ prolapse and urinary incontinence and reported that the median number of opioid tablets consumed 2 weeks after a minimally invasive urogynecologic surgery was less than 10. Sixty six percent of patients reported having excess opioid tablets at 2 weeks postoperatively and 42% of patients reported that they were going to keep their excess tablets for future use.¹¹ Swenson et al. evaluated 50 patients who underwent minimally invasive urogynecologic surgery for the indication of pelvic organ prolapse and found that the median number of opioid tablets consumed was 13, and that participants only used one third of the amount prescribed.¹² Bates et al. surveyed adult patients who underwent surgery in a urology practice and showed that only 58% of the prescribed pain medication was used and 67% of participants reported having excess medication⁶. Of note, 92% of patients within the study reported receiving no formal disposal instructions for excess opioid medication and of those patients with leftover medication, 91% kept the medication at home. Bartels et al. found that 53% of participants reported taking fewer than five opioid tablets following a cesarean delivery.⁷

3. Describe the purpose, specific aims or objectives. Specify the hypotheses or research questions to be studied.

The purpose of this study would be to evaluate whether a preoperative educational pamphlet addressing the risks and side effects of opioid medications would reduce postoperative opioid consumption after common urogynecologic surgeries for the indication of pelvic organ prolapse. The hypothesis is that patients who receive the preoperative opioid education would consume less opioid tablets after their surgeries.

Additionally, the effect of the preoperative opioid educational intervention on postoperative patient storage patterns and compliance with FDA-recommended disposal patterns of opioid medications

would be evaluated. The hypothesis is that patients who receive the opioid education would have higher rates of safe storage patterns (out of sight, in a locked area) and FDA-recommended disposal patterns (return to a FDA-approved distribution center, mix with an unpalatable substance before disposing in the trash, or flushing down the sink or toilet) compared to patients who did not receive the opioid educational intervention.

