The pattern of postoperative opioid consumption will be evaluated at 2 weeks and 6 weeks after the surgery and will be compared between subjects who underwent preoperative opioid education versus those who did not. The hypothesis is that subjects who receive the preoperative opioid education will be less likely to consume opioid tablets after 2 weeks compared to subjects who did not receive the educational intervention.

The rates of prescription refills 12 months after the surgery will be evaluated and compared between subjects who underwent preoperative opioid education versus those who did not. The hypothesis is that subjects who receive preoperative opioid education will be less likely to have opioid refills within the first 12 months postoperatively compared to subjects who did not receive the educational intervention.

The postoperative opioid consumption between subjects with particular clinical conditions (preoperative opioid use, active tobacco use, the presence of a chronic pain syndrome, anxiety, depression) will be compared to subjects without these conditions. The hypothesis is that subjects with these clinical conditions will have higher postoperative opioid consumption rates, including higher rates of opioid prescription refills within 12 months after surgery, compared to subjects without these conditions.

The subjects' opinions about the adequacy of their initial postoperative opioid prescriptions will be compared between subjects who received the preoperative educational intervention versus those who did not. The hypothesis is that subjects who received the preoperative educational intervention will be more likely to answer that their opioid prescription was "more than adequate" or "adequate" compared to subjects who did not receive the educational intervention. The subjects' opinions regarding the adequacy of their initial postoperative opioid prescriptions will be compared between subjects with particular clinical conditions (chronic pain syndromes, anxiety, depression, active tobacco use, and preoperative opioid use) to subjects without these conditions. The hypothesis is that subjects with the clinical conditions will be more likely to answer "less than adequate" regarding their postoperative opioid prescriptions compared to subjects without these clinical conditions.

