Not applicable: Individual results will not be shared with subjects.

3. Describe whether overall study results will be shared with subjects.
4. Explain how results will be shared.

Not applicable: Final study results will not be shared with subjects.

I. Statistical Considerations

1. Statistical Analysis Plan: Describe the statistical method(s) for the stated specific aims and hypotheses. *Your analysis plans should match the stated study specific aims and hypotheses in Section 1.*

Not applicable: A statistical analysis plan is not appropriate for this qualitative study design. Plan for assessing study results:

2. Describe the primary statistical method(s) that will be used to analyze the primary outcome(s) or endpoints.

A t-test will be used to analyze the primary outcome, which will compare the mean number of opioid tablets consumed by subjects in the two study arms.

3. Describe the secondary statistical method(s) that will be used to analyze the secondary outcome(s) or endpoints.

A t-test will be used to compare the mean number of opioid tablets consumed at 6 weeks and 12 weeks postoperatively between subjects in the two study arms. A t-test will be used to compare the modified surgical pain score answers between subjects in the two study arms at the preoperative assessment, 2 weeks postoperatively, and 6 weeks postoperatively. Fisher's exact test will be used to compare the subjects' answers to standardized questions on the preoperative and postoperative opioid education study surveys (categorical response variables) between the two study arms. A Mann-Whitney test will be used to compare the number of opioid prescription refills at 2 weeks, 6 weeks, 12 weeks, and 12 months postoperatively between subjects in the two study arms. A Fisher exact test will be used to compare the rates of intraoperative and postoperative complications between subjects in the two study arms. A t-test will be used to compare the length of time to postoperative discharge, time to postoperative foley catheter removal, and length of the surgery between subjects in the two study

arms.

4. If appropriate describe secondary or post hoc analyses of primary outcome(s) or other exploratory analysis.

N/A

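### The adequacy hypothesis is a two-level rate, but the survey analysis gives no grouping of answers; read as written, it is a three-category Fisher test that can be significant when that rate is equal in both arms

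*Combined protocol and SAP*

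**What the plan says.** Section 6.I, item 3 (secondary methods) specifies Fisher's exact test for "answers to standardized questions on the preoperative and postoperative opioid education study surveys (categorical response variables) between the two study arms". It names no event for any survey item and no grouping of answers.

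The hypotheses are in Section 1, item 3:

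- **Adequacy.** Educated subjects "will be more likely to answer that their opioid prescription was" either 'more than adequate' or 'adequate'. The next hypothesis, on clinical conditions, names a third answer, 'less than adequate'.
- **Storage and disposal.** Educated subjects are expected to have "higher rates of safe storage patterns (out of sight, in a locked area) and FDA-recommended disposal patterns".

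The form's instruction at Section 6.I, item 1 reads "Your analysis plans should match the stated study specific aims and hypotheses in Section 1". Section 6.C, item 3 lists the postoperative survey as investigator-authored. Its items and response options are not in the documents.

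**The concern.** The adequacy hypothesis merges two of the three named answers. A test on all three asks whether the answer distribution differs in any way, so a significant result need not involve the share answering 'less than adequate', which is the only share the hypothesis concerns.

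The shift that causes trouble is a plausible one. Section 6.C, item 1 gives both arms standardized postoperative prescriptions, and the main hypothesis is that educated women take fewer tablets. If that is true, more tablets are left over, and some women who would have answered 'adequate' may answer 'more than adequate'. An effective intervention could thus yield a significant adequacy p-value while the hypothesised rate stays the same. This mechanism is an inference from the design; the documents do not state it.

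**Working it through.** **The plan's own figure.** Section 6.I, item 5 gives 63 per arm for 80% power at 0.05 and a difference of 0.5 SD. Check: n = 2(1.96 + 0.8416)² / 0.5² = 62.8, so 63. This reproduces. It concerns the primary outcome; no figure is given for the survey items.

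**Inputs.** 63 evaluable per arm and alpha 0.05 come from Section 6.I, item 5; two-sided testing is assumed, since sidedness is not stated. The three answers come from Section 1, item 3. All answer splits are assumptions. Splits are given as more than adequate / adequate / less than adequate.

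**Tests compared.**

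- Three-category: exact Fisher (Freeman-Halton) test on the 2x3 table. The p-value is the sum of the probabilities of all tables with the same margins that are no more probable than the observed one.
- Two-level: Fisher's exact test on the 2x2 table of 'adequate' or better against 'less than adequate'.

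**One worked table (assumed counts).** Intervention 36/17/10, control 18/35/10. The hypothesised rate is (36 + 17)/63 = 53/63 = 84.1% in the intervention arm and (18 + 35)/63 = 53/63 = 84.1% in the control arm. The three-category test gives p = 0.0024; the 2x2 test gives p = 1.00.

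**Rejection rates.** 'Less than adequate' is 10% in both arms, so the hypothesised rate is 90% in both; 6,000 simulated trials per row. The 95% simulation error is at most about 1.3 points.

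| Control | Intervention | Shift | 3-category | 2x2 |
|---|---|---|---|---|
| 30/60/10 | 30/60/10 | 0 points | 4.8% | 2.6% |
| 30/60/10 | 40/50/10 | 10 points | 17% | 1.9% |
| 30/60/10 | 50/40/10 | 20 points | 56% | 2.1% |
| 30/60/10 | 55/35/10 | 25 points | 77% | 2.3% |

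The 2x2 column estimates one quantity in every row. Full enumeration puts it at 2.3%.

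**Power when the rate really differs.** For 35/40/25 v 43/49/8, power is 64% (three-category) and 67% (2x2). For 40/50/10 v 40/30/30 the order reverses: 81% and 76%. Power gives no general reason to prefer either test.

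**The case against.** The strongest reply is that the plan never says the answers are tested ungrouped. A yes/no recode is also categorical, Section 1 already supplies the grouping for adequacy, and the form asks that analyses match the hypotheses. On that reading the 2x2 test may be what was meant. This stands in part: testing the ungrouped answers is the natural reading, but not the only one. The same paragraph speaks of comparing rates for complications and answers for survey items. If the text is instead open, the choice between two tests that can disagree as widely as p = 0.0024 and p = 1.00 is left until after the data are seen, in a non-blinded trial. Either reading calls for the same sentence.

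A second reply is that survey responses are themselves a listed secondary outcome (Section 1, item 4), so testing their distribution is legitimate. That stands. With identical arms the three-category test rejects in 4.8% of trials, so it keeps its level. A reader might infer that the plan uses an invalid test or inflates type I error. It does not: in the shifted rows the answers truly differ between arms, just not in the hypothesised rate.

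A third reply is that the percentages depend on chosen splits. That also stands. They show what can happen, not what will happen here.

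A reader might also infer that the storage and disposal analyses have the same fault, with a move between two unsafe places counted as a difference. The documents do not support this. The response options are not shown, and with yes/no items the problem would not arise.

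**Conclusion.** For adequacy the point holds. Section 1 names three answers and states a two-level hypothesis, and the analysis section gives no grouping. Following the test as written can produce a significant p-value that does not bear on the hypothesis. Under the assumed splits, with equal hypothesised rates, this happens in about 17% to 77% of trials for shifts of 10 to 25 points, against about 2% for the 2x2 test. The figures rest on 63 evaluable per arm, two-sided 0.05, and no change at all in 'less than adequate'.

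For storage and disposal the point is conditional on items that are not shown. One gap there is visible all the same: the definition of safe storage does not say whether out of sight and locked are both required.

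These are secondary outcomes. The primary t-test and the sample size are unaffected. The change is worth making, but it does not threaten the trial's main result.

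**What to change.** In Section 6.I, item 3, add that the adequacy hypothesis is tested by a 2x2 Fisher exact test of 'adequate' or 'more than adequate' against 'less than adequate', with the risk difference and its 95% CI. The sign of the risk difference shows the direction that the hypothesis specifies. State which visit the test refers to, since the survey is given at 2 and 6 weeks. Report the full answer distribution by arm as supportive. A test on it need not be barred, provided it is not presented as the test of this hypothesis.

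If the storage and disposal items have more than two answers, code each as yes/no from the Section 1 definitions and analyse it in the same way. State whether safe storage requires both out of sight and locked.

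The cost is a few sentences and a recode of answers already collected; no new data or patients are needed. The small downside is that the 2x2 test ignores movement between 'adequate' and 'more than adequate', which the supportive table still shows.

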Study design, identifying potential study participants, finalizing informed consent (reviewing, answering/asking questions, confirming competency, as necessary, and signing/confirming the informed consent), providing standardized patient education about opioid medications, administering patient questionnaires, and quantifying remaining postoperative opioid tablets.

[name] is a Female Pelvic and Reconstructive Surgery fellow at UC Irvine. She completed her obstetrics and gynecology residency at Johns Hopkins University. She is an author on six scientific manuscripts in the literature to date, including four manuscripts as the first author.

Research Personnel:

Name and Degree: [name]

Position/Title and Department: Junior Specialist, Obstetrics & Gynecology

Research Assistant, Obstetrics & Gynecology Department

Team Member will: Screen/Recruit Finalize Informed Consent

Perform Research Activities Access subject identifiable data

List the research activities/procedures to be performed and the individual's relevant qualifications (training, experience):

Administering patient questionnaires and quantifying remaining postoperative opioid tablets.

[name] is a research assistant within the department of Obstetrics and Gynecology at UC Irvine Medical Center. She graduated from UC Berkeley in 2017 and is in the process of applying to medical school.

SECTION 3: SUBJECT POPULATION(S) (INDIVIDUALS/RECORDS/SPECIMENS)

A. Subjects To Be Enrolled on this UCI protocol (Persons/Records/Biospecimens)

1. Complete the table of subject enrollments below.
2. If the study involves the use of existing records or biological specimens, specify the maximum number to be reviewed/collected and the number needed to address the research question.

| Category/Group (e.g., adults, controls, parents, children) | Age Range (e.g., 7-12, 13–17, adults) | Maximum Number to be Consented or Reviewed/Collected (include withdrawals and screen failures) | Number Expected to Complete the Study or Needed to Address the Research Question |
|--|---|--|---|
| Adults in intervention arm | 18-99 years old | 73 | 63 |
| Adults in control arm | 18-99 years old | 73 | 63 |
| | | | |
| | | | |
| Total: 146 | | | |

B. Overall Study Sample Size

If this is a multi-site study, provide the total number of subjects to be enrolled from all sites.

Total number of subjects across all sites: 146

C. Eligibility Criteria

1. Identify the criteria for inclusion and exclusion.

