During the 2 week postoperative visit, the remaining opioid tablets will be counted and recorded by a co-investigator. The patient will complete the modified surgical pain score and postoperative opioid education study survey. The UC Irvine electronic medical record system and CURES 2.0 Database will be queried to evaluate for additional opioid prescriptions since the time of surgery. Patients randomized to the intervention arm will receive the second opioid informational pamphlet, which will be reviewed by a co-investigator.

During the 6 week postoperative visit, the patient will complete the modified surgical pain score and postoperative opioid education study survey. The UC Irvine electronic medical record system and CURES 2.0 Database will be queried to evaluate for additional opioid prescriptions since the time of surgery. The patients' electronic medical records will be reviewed after the 6 week postoperative visit to evaluate for postoperative complications.

Twelve weeks after the surgery, the UC Irvine electronic medical record system and CURES 2.0 Database will be queried to evaluate for additional opioid prescriptions since the time of surgery.

If a patient fails to follow up for a postoperative visit, at least two attempts will be made to contact the patient via telephone to collect opioid pill counts and have the patient verbally complete the modified

surgical pain score and postoperative opioid education study survey. Initial statistical analysis will be performed after the 12 week postoperative opioid refill assessment

Twelve months after the surgery, the UC Irvine electronic medical record system and CURES 2.0 Database will be queried to evaluate for additional opioid prescriptions since the time of surgery. Additional statistical analysis will be performed after the 12 month opioid refill prescriptions have been evaluated.

While this is a multi-site trial involving subjects from UC Irvine and Kaiser Permanente Orange County – Irvine, only deidentified data will be uploaded into the REDCap data management system. The lead investigator will maintain a separate key containing patient health information for subjects from both sites, which will be utilized to evaluate for additional opioid prescriptions 12 months after the surgery. Co-investigators from both study sites will not have access to identifiable data from subjects that were not recruited from their particular study site.

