5. Sample Size Determination: Explain how the overall target sample size was determined (e.g., power analysis; precision estimation), providing justification of the effect size for the primary outcome based on preliminary data, current knowledge/literature and/or cost consideration; if appropriate, provide sample size justification for secondary outcomes. Power analysis should (at least) match the primary outcome/endpoint.

A power calculation indicates that a sample size of 63 subjects in each arm is necessary to achieve 80% power to detect a mean difference of 5 opioid tablets consumed with a significance level of 0.05. This difference is equivalent to a difference of 0.5 SD. Given an anticipated attrition rate of 15%, 73 subjects will be recruited into each arm of the study. Current literature suggests that the mean number of opioid tablets consumed by patients undergoing urogynecologic surgeries for pelvic organ prolapse ranges between 2-13 tablets and therefore, this study is powered to detect a 50% decrease in postoperative opioid tablet consumption if we anticipate that patients who do not undergo the educational intervention will consume a mean of 10 tablets.

SECTION 7: RISK ASSESSMENT AND POSSIBLE BENEFITS

A. Risk Assessment

1. Indicate the appropriate level of review of this study, based upon your risk assessment.

This study involves greater than minimal risk to subjects and requires Full Committee review.

This study involves no more than minimal risk and qualifies as [Expedited research](#).

2. If this study involves no more than minimal risk, provide justification for the level of review and for all applicable Expedited Categories you have chosen.

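### Recruiting 73 per arm with 15% attrition leaves about 62, one short of the 63 per arm the plan requires (minor)

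*Combined protocol and SAP*

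**What the plan says.** Section 6.I.5 (Sample Size Determination) states: "A power calculation indicates that a sample size of 63 subjects in each arm is necessary to achieve 80% power". The target is a mean difference of 5 tablets at a significance level of 0.05, and the section adds: "This difference is equivalent to a difference of 0.5 SD". The attrition step follows: "Given an anticipated attrition rate of 15%, 73 subjects will be recruited into each arm of the study".

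The table in Section 3.A repeats these figures for each arm. It enters 73 under the column headed "Maximum Number to be Consented or Reviewed/Collected (include withdrawals and screen failures)" and 63 under the column headed "Number Expected to Complete the Study or Needed to Address the Research Question". Section 3.B gives the overall figure: "Total number of subjects across all sites: 146".

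For the analysis, Section 6.I.2 states: "A t-test will be used to analyze the primary outcome". For patients who miss a postoperative visit, Section 6.C.1 provides that "at least two attempts will be made to contact the patient via telephone to collect opioid pill counts".

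**The concern.** The 73 is presented as the number that protects the required 63 against 15% attrition. Read in the ordinary way, as 15% of those recruited, the figures 63, 15% and 73 cannot all hold.

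The enrolment table leaves no slack. Its 73 is a ceiling on consents and already includes withdrawals and screen failures, so the 73 − 63 = 10 spare places per arm must absorb every loss after consent. Consent and randomisation can take place as early as the consultation visit (Section 6.C.1), and a cancelled operation is an exclusion criterion (Section 3.C). Some of those places may therefore be used up before surgery.

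What is at stake is mainly the accuracy of the sample-size justification. A larger slip of this kind would leave a trial short of its stated power; here the shortfall is about one patient per arm.

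**Working it through.** **Inputs.** From Section 6.I.5: difference 5 tablets, equal to 0.5 SD, so SD = 5/0.5 = 10 tablets; significance level 0.05; power 80%; 63 per arm needed; attrition 15%; 73 per arm recruited. From Section 3.B: 146 in total. From Section 6.I.2: the primary test is a t-test. Sidedness is not stated, so two-sided is an assumption, checked in step 1.

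**1. Reproduce the 63.** Normal approximation, n per arm = 2(z_α + z_β)²/d², with d = 0.5:

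- Two-sided: 2 × (1.960 + 0.842)²/0.25 = 62.79, rounded up to 63. This matches the plan.
- One-sided: 2 × (1.645 + 0.842)²/0.25 = 49.46, rounded up to 50. This does not match.

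The plan's figure is therefore the two-sided normal-approximation size. The same calculation for a t-test gives 63.77, rounded up to 64.

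**2. Reproduce the 73.** 63 × (1 + 0.15) = 72.45, rounded up to 73. This matches the plan. Dividing by the retention rate gives 63/(1 − 0.15) = 74.12, rounded up to 75, which does not.

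**3. Apply the stated attrition to the stated recruitment.**

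| Recruited per arm | Remaining at 15% attrition |
|---|---|
| 73 | 73 × 0.85 = 62.05 |
| 74 | 74 × 0.85 = 62.90 |
| 75 | 75 × 0.85 = 63.75 |

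In total, 146 × 0.85 = 124.1, against 2 × 63 = 126. The highest attrition at which 73 still leaves 63 is 1 − 63/73 = 10/73 = 13.7%.

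**4. Effect on power** for 5 tablets, two-sided 0.05. The normal approximation is Φ(0.5 × √(n/2) − 1.960); the t-test figures use the noncentral t distribution.

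| Per arm | Normal approximation | t-test |
|---|---|---|
| 62 | 79.5% | 78.9% |
| 63 | 80.1% | 79.5% |
| 64 | 80.7% | 80.1% |

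Going from 63 to 62 costs about 0.6 percentage points by either method.

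**5. Detectable difference at 80% power with 62 per arm.** Normal approximation: (1.960 + 0.842) × 10 × √(2/62) = 5.03 tablets. t-test: 0.5072 SD × 10 = 5.07 tablets. The plan states 5.

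**6. Chance of keeping 63.** If losses are independent at 15% (an assumption), an arm of 73 keeps at least 63 with binomial probability 0.457, and an arm of 75 with probability 0.668.

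**The case against.** The strongest reply is that this does not matter. Losing one patient per arm has the same effect on power as an SD of 10 × √(63/62) = 10.08 instead of 10. The plan fixes the SD only through the 0.5 SD statement and quotes a literature range of 2 to 13 tablets for mean consumption, so the uncertainty in the SD is far larger than this. That stands, and it is why the point is minor. The binomial figures should not be read as a measure of harm either: even 75 per arm would miss 63 about one time in three.

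A second reply is that the plan never says outright that 63 will remain, gives no denominator for the 15%, and heads its table column with a choice between expected and needed. The 63 is indeed correct as the number needed. But 15% of those recruited is the natural reading of attrition, and the power sentence offers 73 as the answer to it.

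A third reply is that the primary outcome is measured at 2 weeks, active participation runs to 6 weeks, and missed visits are followed up by telephone, so fewer than 15% may lack the primary outcome. That may prove true, and a shortfall in the primary analysis is not established. It does not make the sentence correct, because the plan gives no lower rate for the 2-week outcome.

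Finally, the fall from 80.1% (normal approximation, 63) to 78.9% (t-test, 62) has two causes. About half comes from the change of method and only about half from attrition. The corrected wording should keep the two apart.

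**Conclusion.** The statement is wrong as written, and the error is minor. At the stated 15%, recruiting 73 per arm leaves about 62, not 63; meeting 63 would take 75 per arm or attrition of no more than 13.7%. The likely cause is adding 15% to the required number instead of dividing by 0.85, but that is an inference from the figures.

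The cost is about 0.6 percentage points of power and a detectable difference of 5.03 to 5.07 tablets instead of 5. The trial is not materially underpowered on this account.

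The attrition arithmetic rests only on reading 15% as a share of those recruited. The power figures also assume a two-sided test, which is the reading that reproduces 63, and an SD of 10 tablets.

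**What to change.** Keep 73 per arm and 146 in total, and correct the wording of Section 6.I.5. Suggested text, if 15% remains the expected attrition:

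> Assuming a two-sided 0.05 test, the normal-approximation size for 80% power is 63 per arm (64 for the t-test). With 73 recruited per arm and 15% attrition, about 62 per arm will remain, giving about 79% power with the planned t-test to detect a difference of 5 tablets (0.5 SD).

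In the Section 3.A table, label 63 as the number needed and give about 62 as the number expected to complete.

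An alternative is to keep 63 and 80% and state that 73 per arm suffices if attrition does not exceed about 13.7% (10 of 73). Use this only if the investigators have their own grounds to expect a rate that low; the documents give none, and the rate should not be chosen to fit the number.

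Either change is wording only and adds no patients. Under the first, stated power goes from 80% to about 79%, partly because it is now quoted for the t-test. Under the alternative, only the attrition assumption changes. Recruiting 75 per arm would add 4 patients (150 in total), which a gain of about 0.6 percentage points does not call for.
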